3.6 Patients Replacement

According to the patient number calculation, 136 patients have to be allocated and 128 of these allocated patients are expected to form the intention-to-treat (ITT) population which included all patients who are included in the trial and have received their first dose of chemotherapy. This implies that about 6% of the patients (n=8) included in the trial are anticipated to be drop-outs before starting chemotherapy. These drop-out patients are not replaced.

Any patient dropping out after receiving his first dose of chemotherapy is part of the ITT population and is not replaced.

4. TRIAL DESIGN

This is a multicenter, randomized, open-label phase III trial for newly diagnosed glioblastoma patients with methylated MGMT promoter in their tumor. The study includes the following steps:

Screening phase (1-3 weeks after resection): Patients with previously untreated GBM are screened for the trial. After obtaining informed consent for determination of MGMT promoter methylation status and reference neuropathology, a block of paraffin-embedded tissue is sent for reference neuropathology review to the Department of Neuropathology, University of Bonn. From there, tissue is sent to MDxHealth, where the MGMT promoter methylation status is determined by methylation-specific PCR.

Baseline and randomization phase (week 3-5 after resection): Baseline examinations are performed. After obtaining the MGMT promoter status and confirmation of GBM histology (for the form to submit reference neuropathology and MGMT testing see appendix 3) and obtaining informed consent for trial participation, inclusion/exclusion criteria are evaluated and documented, patients are randomized for standard TMZ chemotherapy or experimental CCNU/TMZ therapy, both in combination with standard RT. Therapy (i.e. RT) has to start within 2 weeks after randomization and 5 weeks after surgery. A 5 week interval is generally accepted for clinical trials in GBM and does not impair therapeutic efficacy (Blumenthal et al., 2008).

Treatment phase: The treatment phase as well as the follow-up phase of the trial is summarized in figure 1. The treatment phase should start not later than 5 weeks after surgery and not later than 2 weeks after randomization and baseline visit.

[figure not shown]
The trial includes two treatment arms:

Experimental arm (CCNU/TMZ arm; 50% of patients): the first course of CCNU (100 mg/m² day 1) and TMZ (100 mg/m²/day, day 2-6) is started on the first day of RT (60 Gy in 2 Gy fractions, 5 days/week). The following 5 courses are applied 6 weeks after the start of the previous course. In the experimental arm, not more than 6 six week courses can be applied.

Standard arm (TMZ arm; 50% of patients): the first application of TMZ is given on the first day of RT (60 Gy in 2 Gy fractions, 5 days/week). During RT, TMZ is given on a daily base with 75 mg/m²/day (including RT-free weekend days). RT with concomitant TMZ chemotherapy (6 weeks) is followed by a 4 weeks interval without therapy. In week 11 after the initiation of RT, the TMZ block chemotherapy ensues with 6 courses of TMZ 150-200 mg/m² day 1-5 of a 28 day course. It is recommended that TMZ chemotherapy is stopped after application of 6 courses (as suggested by Stupp et al., 2005).

Follow-up phase: After the end of the treatment phase, all patients will be followed by clinical examination and contrast-enhanced MRI every 12 weeks until 3 years after randomization. Follow-up of all patients ends 36 months after the inclusion of the last patient. All patients in the trial are followed until this time point.

Fig.1: Schematic overview of the study

* Laboratory and Clinical examinations, toxicity recording as detailed in table 1

- TMZ 75 mg/m² p.o./die over 6 weeks during RT
- TMZ 150 D200 mg/m² p.o. day 1 D5 of a 28 day course
- Radiotherapy of the tumor region, daily, 30 x 2 Gy
Total dose 60 Gy
- CCNU 100 mg/m² p.o. on day 1 +
TMZ 100 mg/m² p.o./die day 2 -6 of 42 day course

5.1.2 Chemotherapy dosing: general considerations

Deviations between calculated TMZ dose and dose applied of more than 5% are regarded as protocol violations. Also, the body weight of the previous course can be used to calculate the body surface area of the next course if it does not differ by more than 5%. The chemotherapy doses of patients with a body surface area of more than 2.3 m² are all calculated with a body surface area of 2.3 m².

5.1.3 Experimental arm: chemotherapy with CCNU/TMZ

The experimental arm consists of six 42 day-courses of CCNU 100 mg/m²/day (day 1) and TMZ 100 mg/m²/day (day 2-6). The first course starts with the first day of RT. CCNU and TMZ are applied orally. TMZ and CCNU have to be taken on empty stomach meaning at least 2-3h hours after the last meal. At least 30 minutes earlier, a serotonin antagonist such as ondansetron or tropisetron have to be taken as antiemetic. TMZ and CCNU is applied on an outpatient base. The doses of CCNU and TMZ are justified by the previously published phase II trial ([name] et al., 2006; Glas et al., 2009) which used the same doses and which provided the promising results that are the base for the present trial. The next course of CCNU/TMZ can only be started if WBC are >3000/μl, neutrophil counts are >1500/μl and platelets are >100000/μl and in case CTC grade < 2 toxicity. Treatment failure is assumed in case of a delay of more than 6 weeks for the start of the next course of CCNU/TMZ. After progression or treatment failure of a patient the further therapy is applied at the discretion of the treating physician.

5.1.3.1 Dose modifications of CCNU/TMZ

Dosing is based on adverse event (AEs) during the prior treatment cycle. If a patient experiences several adverse events, the recommended dose adjustment is to be based on the toxicity that requires the greatest dose reduction. Dose adjustments are to be made according to the system showing the greatest degree of toxicity. Adverse events will be graded using the NCI Common Terminology Criteria for Adverse Events Version

4.0 (CTCAE). In response to acute toxicity, the dosage of TMZ will be reduced according to the criteria outlined in this section. In any case of hematologic toxicity of grades 3 or 4, it is recommended to obtain RBC, platelets, WBC and a differential blood count at least twice weekly. Leucocytes, ANC and platelets have to be determined at least 7 days after the last G-CSF application or transfusion of platelets.

As in the previous phase II trial, the doses of CCNU and TMZ are individually adjusted in following courses according to white blood cell (WBC) and platelet nadirs during the previous course according to the following scheme:

- In case the nadir (WBC < 1500/ μ l or thrombocytes < 50000/ μ l) occurred after day 25, CCNU will be reduced by one dose level with the dose levels being 100%, 75% and 50% of the initial dose. In case of WBC <1500/ μ l thrombocytes <50000/ μ l at the dose level of 50%, CCNU has to be permanently discontinued.
- Depending on the nadirs during the first 25 days of the previous course TMZ will be decreased to the lower dose levels of 75 mg/m² or 50 mg/m² or increased stepwise to the higher dose levels of 120 mg/m², 150 mg/m² and 200 mg/m² according to the following schedule:
 - reduction by 1 dose level if WBC <1500/ μ l or platelets < 50 000/ μ l;
 - reduction by 2 dose levels if WBC <1000/ μ l or platelets < 25 000/ μ l;
 - increase by 1 dose level if RT was completed and WBC >2500/ μ l and platelets >100000/ μ l.
 - In case of WBC <1500/ μ l or thrombocytes <50000/ μ l at the lowest dose level of 50 mg/m², TMZ has to be permanently discontinued.
- In case of any non-hematological toxicity CTCAE grade 3/4, the substance causing the toxicity will be withheld in further courses and therapy within the trail may continue with the substance not causing the toxicity.

Using this scheme, the individual dose adaptation in subsequent courses allows to apply the individually highest possible dose of chemotherapy which may differ greatly between different patients.

It is allowed to apply erythrocyte and/or thrombocyte transfusions to improve Hb and platelet values. The target Hb value and transfusion trigger value is defined by medical comorbidities at the discretion of the investigator. In case platelets counts or Hb values have been improved by transfusion of platelet or erythrocyte concentrates, the platelet and Hb values have to be stable or increasing for at least 7 days prior to the start of the next course.

5.1.4 Standard arm: concomitant and adjuvant chemotherapy with TMZ

TMZ chemotherapy in the standard arm is applied as described in TMZ product information and as described in the landmark publication by Stupp et al. (2005) which led to the approval of TMZ for first-line therapy in glioma.

Concomitant TMZ chemotherapy is started with the first day of radiotherapy at a dose of 75 mg/m² body surface area daily. The last day of radiotherapy is the last day of TMZ chemotherapy. TMZ is also given on weekends. TMZ can be administered as long as all of the following criteria are fulfilled:

neutrophils $\geq 1500/\mu\text{l}$, thrombocytes $\geq 100000/\mu\text{l}$, non-hematological toxicity \leq grade 1 CTC (except alopecia, nausea and vomiting).

In case of CTC grade 2 toxicity, neutrophils between 500 and 1500/ μl and/or thrombocytes between 10000 and 100000/ μl TMZ has to be interrupted until all of the above mentioned criteria are fulfilled again. Temozolomide has to be discontinued in case of CTC grade 3/4 toxicity, neutrophils $< 500/\mu\text{l}$ and/or thrombocytes $< 10.000/\mu\text{l}$. The adjuvant phase of temozolomide therapy will then be started with the lower dose of 100 mg/m² and increased in subsequent courses in steps of 25 mg/m²/day if no further grade 3/4 hematotoxicity ensues.

In the **adjuvant** phase starting 4 weeks +/- 5 days from the last day of radiotherapy, 6 courses of standard adjuvant TMZ chemotherapy is applied with 150-200 mg/m²/day for 5 days of a 28-day course (standard defined by Stupp et al., 2005). If toxicity has already occurred during the combined therapy, TMZ has to be applied at doses of 100mg/m²/day (dose stage -1). Generally, during the first course of monotherapy 150mg/m²/day temozolomide (dose stage 0) has to be administered, during courses 2-6 200mg/m²/day (dose stage 1), if no toxicity occurred (neutrophils $\geq 1500/\mu\text{l}$, thrombocytes $\geq 100000/\mu\text{l}$ and CTC ≤ 2 except alopecia, nausea, vomiting). Temozolomide has to be reduced by one dose stage (dose steps are: 75 mg/m², 100 mg/m², 125 mg/m², 150 mg/m² and 200 mg/m²) if neutrophils $< 1000/\mu\text{l}$, thrombocytes $< 50000/\mu\text{l}$ and/or non-hematological toxicity CTC=3 attributed to TMZ. Temozolomide has to be discontinued if intolerable toxicity persists despite dose stage 1 is administered or grade 3 toxicity persists even after dose reduction.

Treatment failure is assumed in case of a delay of more than 6 weeks for the start of the next course of TMZ. After progression or treatment failure of a patient the further therapy is applied at the discretion of the treating physician.

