3.5 Removal of subjects from study / Withdrawal of subjects

An individual patient will be discontinued from study therapy within the study but treated off-study and followed further under the following circumstances:

- There is MRI- defined progressive disease according to modified RANO criteria as determined by central reference neuroradiology
- The patient requests discontinuation.
- The drugs exhibit unacceptable toxicity defined as follows:
 - Delay of the next course for 6 weeks or more due to hematological toxicity
 - Any non-hematological CTCAE grade 3/4 toxicity attributable to CCNU or temozolomide. Those patients may receive temozolomide or CCNU monotherapy, respectively, if toxicity can be clearly attributed to one of the agents
- The patient becomes pregnant.
- Non-compliance

When a patient withdraws prior to completing the study, the reason for withdrawal is to be documented on the CRF and in the source document. Any clinically significant abnormalities persisting at withdrawal will be followed by the investigator until resolution or until reaching a clinically stable endpoint.

All patients who are discontinued from study therapy for any reason have to be followed according to the study protocol with clinical and MRI investigations (see chapter 6.1."Follow-up after completion of the study therapy or withdrawal (every 12 weeks)") until the end of the follow-up-time of the whole trial 3 years after the inclusion of the last patient.

If a patient requests discontinuation of the study therapy and withdraws his/her consent for the trial, the patient is asked to consent to the performance and documentation of the follow-up visits according to the study protocol.

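### Standard arm: Section 5.1.4 and Section 3.5 give different consequences for adjuvant non-hematological grade 3 toxicity, and the dose stages in 5.1.4 do not match its listed steps

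*Protocol*

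**What the plan says.** Section 5.1.4 governs adjuvant TMZ in the standard arm. It numbers three dose stages. After toxicity in the combined phase, "TMZ has to be applied at doses of 100mg/m²/day (dose stage -1"; otherwise "150mg/m²/day temozolomide (dose stage 0) has to be administered, during courses 2-6 200mg/m²/day (dose stage 1), if no toxicity occurred".

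It then gives the reduction rule: "Temozolomide has to be reduced by one dose stage (dose steps are: 75 mg/m², 100 mg/m², 125 mg/m², 150 mg/m² and 200 mg/m²". The triggers are low counts or "non-hematological toxicity CTC=3 attributed to TMZ". The stopping rule follows: "Temozolomide has to be discontinued if intolerable toxicity persists despite dose stage 1 is administered", or if grade 3 toxicity continues once the dose has been lowered.

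Section 3.5 lists, under unacceptable toxicity, "Any non-hematological CTCAE grade 3/4 toxicity attributable to CCNU or temozolomide". The stated consequence is that the patient comes off study therapy but stays in follow-up. The synopsis has the same entry. Both add that such a patient may go on with the other drug alone if one of the two agents is clearly responsible.

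Two further places matter. Section 5.1.2 states: "Deviations between calculated TMZ dose and dose applied of more than 5% are regarded as protocol violations". Section 9.4 plans to describe dose reductions and premature withdrawals.

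**The concern.** One event has two consequences. A standard-arm patient with a first non-hematological grade 3 toxicity from adjuvant TMZ has the dose reduced under Section 5.1.4 and leaves study therapy under Section 3.5 and the synopsis. No clause says which section takes precedence.

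Section 5.1.4 also uses the term dose stage for two different scales, so the size of a one-stage reduction is not fixed at every level.

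The experimental arm does not have the first problem: Section 5.1.3.1 withholds the responsible drug and allows the other to continue, which agrees with Section 3.5. The contradiction therefore sits in the comparator only. It bears on which reductions and withdrawals there count as following the protocol, and on whether sites that acted differently were each compliant.

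**Working it through.** The plan gives no figure to reproduce. The check is a comparison of the texts plus short arithmetic.

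**1. Discontinue or reduce.** Event: non-hematological grade 3 toxicity attributed to TMZ, adjuvant phase, standard arm.

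| Place | Consequence at first occurrence | When TMZ or study therapy stops |
|---|---|---|
| Section 5.1.4 | Reduce by one dose stage | If grade 3 persists after reduction |
| Section 3.5 | End study therapy | At once |
| Synopsis | End study therapy | At once |

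The single-agent exception in Section 3.5 and the synopsis does not remove the conflict. A patient on TMZ alone has no second study drug to continue.

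**2. Size of one dose stage.** Inputs, all from Section 5.1.4:

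- Numbered stages: -1 = 100, 0 = 150, 1 = 200 mg/m².
- Listed steps: 75, 100, 125, 150, 200 mg/m². The steps 75 and 125 carry no stage number, and since -1 comes directly after 0, no whole number is free for 125.

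| Starting dose (mg/m²) | One stage down, numbered | One stage down, listed | Difference (mg/m²) |
|---|---|---|---|
| 200 | 150 | 150 | 0 |
| 150 | 100 | 125 | 25 |

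Relative size of the gap from 150: 25/125 = 20%, or 25/100 = 25%, depending on the base.

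**3. The stage named in the stopping sentence.** By the section's own numbering, stage 1 is 200 mg/m², the highest dose. At that dose the preceding sentence orders a reduction for its listed toxicities, so stopping because toxicity persists at stage 1 does not fit as printed. The term intolerable is not defined there.

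**4. Timing.** Section 6.4 places one year after the last inclusion at 4 months after the end of trial chemotherapy, so chemotherapy ends about 12 - 4 = 8 months after last-patient-in. Section 9.1 reports a blinded analysis 14 months after last-patient-in. Planned chemotherapy was thus expected to have ended about 14 - 8 = 6 months before that analysis.

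**5. Reach into the analyses.** Section 9.3 defines the ITT set by a first dose and the per-protocol set by courses received; dose deviations enter neither. In Section 6.2.2, the discontinuation component of time to treatment failure names only CCNU/TMZ.

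**The case against.** The strongest objection is timing. On the protocol's own dates this version could hardly change anyone's treatment, and judging past doses by newly reconciled wording would hold sites to text that they did not have. That stands. It moves the benefit from dosing to description and classification, and it is why the wording in force at the time should be noted.

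Second, the single-agent sentence in Section 3.5 and the synopsis presupposes the combination, so the rule may have been written with the experimental arm in mind. That is a plausible intention, but neither place says so.

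Third, the reduction sentence puts its list in brackets right after the term dose stage, which favors the listed steps. This narrows the ambiguity without removing it, because the stage numbers a few lines earlier remain.

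A reader might infer more from three points:

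- **The stage 1 sentence proves a contradiction with the reduction rule.** A lost minus sign is plausible, since stage -1 appears earlier in the same section. A typing error or a fault in extracting the text from the PDF cannot be excluded. The triggers also differ in wording.
- **A dose correct on one scale is always a protocol violation on the other**, because 20-25% exceeds the 5% limit. Section 5.1.2 compares calculated with applied dose, next to sentences on body weight and the surface-area cap. It can be read as covering only calculation and administration, not the choice of level.
- **The toxicity rules as a whole cannot be followed.** The step from 200 to 150 mg/m² and the interruption criteria of the concomitant phase can be followed as written.

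**Conclusion.** The point holds within limits. As written, the standard arm has two incompatible consequences for adjuvant non-hematological grade 3 toxicity attributed to TMZ. A one-stage reduction from 150 mg/m² has two possible results, 25 mg/m² (20-25%) apart. The stage named in the stopping sentence needs checking.

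This rests on reading Section 3.5 and the synopsis literally, as applying to both arms, and on taking both the stage numbers and the bracketed steps in Section 5.1.4 at face value.

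A reader might infer that the survival comparison is compromised. The documents do not support that: the ITT overall survival analysis is not directly affected, and patients taken off study therapy remain in follow-up. The documents give no count of affected patients, so the effect on reported reductions and withdrawals cannot be quantified.

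**What to change.** - Reconcile Section 5.1.4, Section 3.5 and the synopsis so that a single rule applies to this toxicity in the standard arm.
- Make one stage numbering match the listed dose steps.
- Check the stage named in the stopping sentence against the source file and correct it if it is a slip.
- Before database closure, record one convention for describing and classifying dose reductions, withdrawals and dose deviations, including whether the 5% rule in Section 5.1.2 covers the choice of dose level. Note which wording sites had when the doses were given.

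Which clinical rule or dose applies is for the sponsor's clinicians to decide. The cost is a protocol clarification and a short written convention; no new data, sample size change or change to the primary analysis is needed.

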5.2 Supply, package, storage and labelling of investigational products

CCNU and TMZ are both commercially available drugs approved for marketing authorization in Germany. Therefore the capsules are prescribed by the treating physician and provided by the local pharmacy. Drugs are to be kept in an appropriate, secure, locked area at the pharmacy of the participating center and are supplied on the day of intake by the pharmacy. CCNU will be taken by the patient in the hospital under supervision of study personnel. TMZ (day 2-6 of each course) is distributed by the trial center and taken on an outpatient base. The investigator, or a responsible party designated by the investigator, will maintain a careful record of the inventory and disposition of all drugs received using the Drug Accountability Record form. Since this is an open study and drugs are approved for marketing authorization no labelling will be performed. In this study CCNU is used in label. Temozolomide is only approved to be given in a monotherapy. Since in the experimental arm a combined therapy consisting of Lomustine + Temozolomide is provided, Temozolomide in the experimental arm is used off label. This combined therapy has been used before in a non-randomized clinical trial leading to an improved survival by acceptable toxicity ([name] et al 2006), thereby justifying the combination of both drugs and establishing the rational for this clinical trial (for details see chapter 1).

Temozolomide

TMZ is supplied in capsules of the following p.o. dosage strengths: 5 mg, 20 mg, 100 mg, 140 mg, 180 mg and 250 mg. Each capsule contains drug substance in combination with lactose, colloidal silicon dioxide, sodium starch glycolate, tartaric acid, and stearic acid. The capsule shells contain gelatin, titanium dioxide, and sodium lauryl sulfate. The capsules should be stored as indicated in the valid SmPC. Capsules are stable for at least 24 months when stored in amber glass bottles at this temperature. Patients are supplied with TMZ by the local investigator. TMZ as well as the combination of TMZ and CCNU are taken on an outpatient base. If vomiting occurs

during the course of treatment, no redosing of the patient is allowed before the next scheduled dose. The capsules should be taken on an empty stomach, therefore a minimum of 3 hours after a meal and with no food ingestion for 1 hour after TMZ and CCNU administration.

CCNU

Compound name: Cecenu®. A capsule contains 40 mg CCNU in combination with wheat starch, lactose, talcum, magnesiumstearat, gelatine, titanium dioxide and indigocarmin. The capsules should be stored as indicated in the valid SmPC.. Capsules are stable for 36 months when stored in amber glass bottles at this temperature. Cecenu® is manufactured by Medac. Patients will be instructed to swallow the capsules whole, in rapid succession, without chewing them. If vomiting occurs during the course of treatment, no redosing of the patient is allowed before the next scheduled dose. The capsules are recommended to be taken before nighttime or 3 hours after a meal.

